## 17.6. B CELL RECOVERY

B cell recovery is defined as “peripheral B cell counts that have returned to at least 50% baseline values or higher or equal to the lower limit of normal”. Note that B-cell counts need to be depleted (defined as CD19+ B cell count below 20 cells/μL) for each subject before recovery is assessed. The incidence of B cell recovery and CD19+ B cell count per patient will be summarized at each visit and overall, by treatment group. Listings for B cell recovery data and CD19+ B cell count by patient will be provided. A plot for proportion of patients achieving B cell recovery over time by treatment group will be displayed.

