Clinical chemistry: creatinine, alkaline phosphatase, total bilirubin, AST, ALT, total protein, albumin, calcium, BUN, phosphorus, uric acid, and electrolytes (sodium, potassium, chloride).
Hematology: hemoglobin, hematocrit, platelets, white blood cells with differentiation, and neutrophils (absolute counts).
Urinalysis: glucose, protein, blood and leukocytes.
- r To be performed by the local laboratory. Screening performed to confirm negative serology for HIV and HCV. HIV screening test will be performed according to local practice and local regulatory guidance. Patients who are confirmed positive and those who have active infections will be excluded from the participation in the study.
- s Screen all patients for HBV infection by measuring HBsAg and anti-HBcAb. Patients who are confirmed positive for chronic hepatitis B infection (defined as positive HBsAg serology) and those who have active infections will be excluded from the participation in the study. Patients with occult or prior hepatitis B infection (defined as positive total HBcAb and negative HBsAg) may be included if HBV DNA is <20 IU/mL (or 112 copies/mL) by PCR test. These HBV patients must be willing to undergo PCR HBV DNA testing (to be performed by the local laboratory) during study and may participate following consultation with a hepatitis expert regarding monitoring and use of HBV antiviral therapy, and provided that they agree to receive treatment as indicated. An HBV re-test will be performed at each study visit from Week 5 onwards, and at the discretion of the Investigator.
- t To be performed at screening unless obtained within 3 months prior to Day 1. TB screening test will be performed if required by local regulatory guidance or at the investigator's discretion. A chest X-ray will be required for all patients with a positive TB test to confirm there is no active TB.
- u Blood PK samples will be collected **from the PK/PD sub-population of patients only**. Please refer to information about sampling time points as below:
Days 1, 8, 15, and 22: 0 hours (pre-dose), and at the end of infusion (\pm 10 minutes windows)
For all other time points: Infusion start time on Day 1 (\pm 6 hours window)
- v Blood samples for CD19+ B-cell counts will be collected, **from the PK/PD sub-population of patients only**, at the same time points for PK sampling plus Weeks 36 and 52.

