8.9 Safety

All safety analyses will be performed using the SAF. The safety variables are defined as follows:

- SAEs, AEs, AESIs, and ADRs
- Clinical laboratory parameters including hematology, chemistry, and urinalysis
- Concomitant medication use
- Vital signs, ECG, and physical examination.
- The proportion of patients achieving B-cell recovery (i.e. \geq lower limit of normal (LLN) or at least 50% of the baseline value) at Week 12, 20, 28, 36 and 52

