8.9.5 B-cell recovery

The proportion of patients achieving B-cell recovery (i.e. \geq lower limit of normal (LLN) or at least 50% of the baseline value) at Week 12, 20, 28, 36 and 52

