## **17. Safety Outcomes**

All outputs for safety outcomes will be based on the SAF.

There will be no statistical comparisons between the treatment groups for safety data.

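### SAP 17.6 can score B-cell recovery at a count it also defines as depleted when baseline is below 40 cells/µL, and it states no denominator for an endpoint measured only in the PK/PD sub-population

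*SAP*

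**What the plan says.** **Recovery.** SAP 17.6 defines it as "peripheral B cell counts that have returned to at least 50% baseline values or higher or equal to the lower limit of normal". Either limb is enough.

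**Depletion.** The next sentence reads: "Note that B-cell counts need to be depleted (defined as CD19+ B cell count below 20 cells/μL) for each subject before recovery is assessed". It is an entry condition only. The section does not say that the depleted count must be post-dose, or that a recovered count must be 20 or above.

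**Protocol.** Sections 2.3.7, 8.9 and 8.9.5 carry the same two limbs ("The proportion of patients achieving B-cell recovery" at Weeks 12, 20, 28, 36 and 52) without a depletion condition. SAP 2.6, which lists the changes from the protocol, does not mention that one was added.

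**Planned output.** "The incidence of B cell recovery and CD19+ B cell count per patient will be summarized at each visit and overall, by treatment group". No denominator is given.

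**Analysis set.** Protocol 8.9 lists B-cell recovery among the safety variables and states "All safety analyses will be performed using the SAF". SAP 17 agrees: "All outputs for safety outcomes will be based on the SAF". The SAF is every randomized patient with at least one dose.

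**Who is measured.** Protocol Table 1, footnote v: "Blood samples for CD19+ B-cell counts will be collected", and the footnote restricts this to the PK/PD sub-population.

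**The concern.** Depletion is an absolute threshold, while one limb of recovery is relative to baseline. For a patient who starts low, the relative limb falls under the absolute threshold, and the same count earns both labels. Recovery is a named safety endpoint with its own summary by visit and overall, a listing and a plot. Two competent programmers could therefore produce different tables from the same text.

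The analysis set adds a second ambiguity. More than half of the planned SAF has no scheduled CD19+ count, and 17.6 does not say whether those patients are left out or counted as not recovered. Elsewhere the SAP is explicit: section 18.1 gives ADA incidence an available-results denominator, and section 2.6 recognises that IgG and IgM are measured in the whole SAF while keeping CD19+ in the PDS definition.

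**Working it through.** The plan states no sample size, power or expected proportion for this endpoint, so there is no figure to reproduce. The check is logic and simple arithmetic.

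**Inputs**
- Depletion: count c < 20 cells/µL (SAP 17.6).
- Recovery: c ≥ 0.5 × b, or c ≥ LLN, where b is baseline (SAP 17.6).
- CD19+ values below quantification are set to zero for all summaries (SAP 14.1).
- 308 patients planned in all; 134 in the PK/PD sub-population, 67 per arm (protocol 8.4 and synopsis; SAP 2.3).
- LLN: not in the documents. Assumed at 20, 50, 100 and 200 cells/µL to see whether it matters.

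**Step 1: overlap of the two labels.** Through the 50% limb, a count meets both labels when 0.5 × b ≤ c < 20. Such a c exists only if 0.5 × b < 20, that is, b < 40. With whole-number counts, the highest baseline with an overlap is 38. The result is the same at all four assumed LLN values. The LLN limb overlaps only if the LLN itself is below 20.

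| Baseline (cells/µL) | Whole-number counts both recovered and depleted |
|---|---|
| 0 (below quantification) | 0 to 19 |
| 10 | 5 to 19 |
| 20 | 10 to 19 |
| 30 | 15 to 19 |
| 38 | 19 |
| 40 or more | none |

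A patient with baseline 30, nadir 0 and a later count of 16 is recovered (16 ≥ 15) and still depleted (16 < 20).

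**Step 2: baselines below 20.** A baseline of 15 meets the depletion definition before any drug. If the Week 12 count is also 15, the literal rule gives depletion followed by recovery with no change at all. A baseline set to zero is recovered at zero, because 0 ≥ 0.5 × 0.

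**Step 3: how many patients.** This cannot be derived. Purely as an illustration, if 0%, 5% or 20% of the 134 started below 40, that would be 0, about 7 (0.05 × 134 = 6.7) or about 27 (0.20 × 134 = 26.8) patients. Nothing in the documents favours any of these shares. A patient is misclassified only if a visit count also falls in the overlap.

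**Step 4: denominator.** Assuming every randomized patient is dosed, 308 − 134 = 174 patients (174/308 = 56.5%) have no scheduled CD19+ count. If all 308 were the denominator and unmeasured patients counted as not recovered, every proportion would be multiplied by 134/308 = 0.435:

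| Recovery among measured patients | Reported on full SAF |
|---|---|
| 30% | 13.1% |
| 50% | 21.8% |
| 70% | 30.5% |
| 90% | 39.2% |
| 100% | 43.5% |

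A 15-point difference between arms would show as 15 × 0.435 = 6.5 points.

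**Step 5: effect of the correction.** Requiring c ≥ 20 removes the overlap. It leaves the 50% limb unchanged for every patient with a baseline of 40 or more.

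**The case against.** A reader might infer that the endpoint is wrong as defined, that recovery will be reported with a ceiling of 43.5%, or that a difference between arms could be hidden. The documents do not support any of these.

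- **Denominator.** The SAP never says that unmeasured patients count as not recovered. Its depletion condition cannot be met without a count, and SAP 6.2 says that missing data are not imputed unless specified. The 43.5% ceiling is therefore the less natural reading. What stands is that the denominator is unstated and the named analysis set does not fit the measurement.
- **Difference between arms.** Randomization is stratified by PK/PD inclusion (SAP 2.2), so any dilution would be about equal in both arms. SAP 17 plans no statistical comparison of safety data. CD19+ counts are summarized and listed by arm, and SAP 14.2 reports CD19+ AUECs to Week 52 with differences and 90% CIs. None of these uses the recovery rule, so a real difference in B-cell return would still be visible.
- **Size.** Very low baselines may be rare. Exclusion criteria 1 and 9 remove patients with prior chemotherapy, rituximab or another monoclonal antibody, and those with immunodeficiency. This is fair; zero affected patients is consistent with the documents.
- **Cost of a floor at 20.** A patient with baseline 22 who returns to 19 (19/22 = 86% of baseline) would not be scored as recovered, although the relative limb exists to recognise return to the patient's own level. The two-limb rule also comes from the protocol. Both points stand, and are met by a separate display and a declared change.

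**Conclusion.** SAP 17.6 is internally inconsistent for patients with a baseline below 40 cells/µL, and under-specified on the denominator. The overlap follows from the SAP's own two thresholds and needs no outside figure. How many patients it touches is unknown, because neither the baseline distribution nor the LLN is given.

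The 0.435 dilution is conditional: it applies only if the full SAF is the denominator, and it rests on the planned 134 and 308 with everyone dosed. The unlisted depletion condition is a plain discrepancy between SAP 17.6 and protocol 8.9.5.

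The endpoint is a descriptive safety summary. The primary equivalence conclusion does not depend on it. The point is a clarification worth making before unblinding, not a flaw in the trial's main inference.

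**What to change.** In SAP 17.6:

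1. Require a post-dose CD19+ count below 20 cells/µL before recovery is assessed, and do not score recovery at any count that still meets that depletion definition.
2. Show patients with a baseline below 20 (including those set to zero) separately. The post-dose requirement alone does not help them, since they can meet it without any fall. List patients with a baseline from 20 to below 40, for whom the added condition changes the 50% limb.
3. Take as denominator at each visit the PK/PD sub-population patients with a baseline count, documented post-dose depletion and a CD19+ result at that visit. Report by arm the number never depleted.
4. In SAP 2.6, declare both the depletion condition and the requirement that a recovered count is no longer depleted, as changes from protocol 8.9.5.

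The cost is SAP text and table programming, with no new data. The downside is small: a patient with a very low baseline who returns close to it but stays below 20 is not scored as recovered. The separate display and listing make such patients visible.

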## 2.6. CHANGES TO ANALYSIS FROM PROTOCOL

The following updates were made:

- The PK and PD analysis sets were updated to include subjects that received at least one dose of the study drug. The PD analysis set were updated to only include subjects that have at least one measured PD variable (CD19+ B-cell count). IgM and IgG were removed from the definition of the PDS since those PD variables are measured in all subjects in the safety analysis set.
- The following criteria was not considered for the exclusion of patients from the Per Protocol Set (PPS):
  - Patient did not have available response assessment at Week 28

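### SAP 17.6 assesses B-cell recovery only after depletion below 20 cells/µL, a condition that the protocol lacks and SAP 2.6 does not declare, with no depletion rate or denominator planned

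*SAP*

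**What the plan says.** **The endpoint in the protocol.** The synopsis and sections 2.3.7, 8.9 and 8.9.5 give the same endpoint: "The proportion of patients achieving B-cell recovery". It is defined by a threshold and a list of visits, "lower limit of normal (LLN) or at least 50% of the baseline value) at Week 12, 20, 28, 36 and 52". None of these places requires the count to have fallen first, and none mentions 20 cells/µL.

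**The endpoint in the SAP.** Section 17.6 keeps the threshold and adds: "Note that B-cell counts need to be depleted (defined as CD19+ B cell count below 20" cells/µL), applied "for each subject before recovery is assessed". The planned outputs are these: "The incidence of B cell recovery and CD19+ B cell count per patient will be summarized at each visit and overall, by treatment group"; "A plot for proportion of patients achieving B cell recovery over time by treatment group will be displayed"; and patient listings. No output gives the number or proportion depleted. The section does not say whether a patient who never falls below 20 leaves the denominator or stays in it as not recovered.

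**Declared changes.** SAP 2.6 begins "The PK and PD analysis sets were updated to include subjects that received at least one dose of the study drug". It then removes IgG and IgM from the definition of the PD set and drops one exclusion criterion from the per-protocol set. B-cell recovery is not mentioned.

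**Who is measured.** SAP 17 bases all safety outputs on the safety set and plans no comparison between arms. Footnote v to Protocol Table 1 limits CD19+ sampling to the PK/PD sub-population, planned at 134 patients (67 per arm).

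**The concern.** Whether a patient's B cells fall below 20 cells/µL depends on the drug received. A recovery rate restricted to patients who got there compares groups selected by a treatment effect and no longer compares the arms as randomised. PD is a secondary objective of this biosimilarity trial, so a difference between arms in the share of patients depleted is itself evidence. The recovery table as planned would not show it.

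The text also leaves room for two different tables. One statistician could drop never-depleted patients, and another could count them as not recovered. Both would be following section 17.6. Because the change is not in SAP 2.6, a reader of the study report would take either table to be the protocol's endpoint.

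**Working it through.** The plan states no figure to reproduce. The check is the comparison of texts above, plus arithmetic on what each rule would report.

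**Inputs.** None of the three rates is in the documents, so all are assumptions:
- d = share of an arm depleted: 98–100% for MabThera, 70–95% for SAIT101.
- r = recovery among depleted patients: 20%, 40% or 60%, equal in both arms.
- q = share of never-depleted patients who meet the recovery threshold: 100% or 50%.

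**Formulas for one arm**
- Protocol rule: d·r + (1 − d)·q
- SAP rule, depleted patients as denominator: r
- SAP rule, all patients as denominator and never-depleted counted as not recovered: d·r

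**Worked case: r = 40%, q = 100%, 98% v 90% depleted (MabThera v SAIT101)**
- Protocol: 0.98 × 0.40 + 0.02 = 41.2%; 0.90 × 0.40 + 0.10 = 46.0%.
- SAP, depleted only: 40% and 40%.
- SAP, all patients: 0.98 × 0.40 = 39.2%; 0.90 × 0.40 = 36.0%.

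**Differences, SAIT101 minus MabThera, in percentage points**

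| Depleted, MabThera v SAIT101 | r | q | Protocol rule | SAP, depleted only | SAP, all patients |
|---|---|---|---|---|---|
| 98% v 90% | 40% | 100% | +4.8 | 0 | −3.2 |
| 98% v 90% | 40% | 50% | +0.8 | 0 | −3.2 |
| 98% v 80% | 40% | 100% | +10.8 | 0 | −7.2 |
| 98% v 80% | 40% | 50% | +1.8 | 0 | −7.2 |
| 98% v 80% | 60% | 50% | −1.8 | 0 | −10.8 |

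The depletion pairs evaluated were 100% v 95%, and 98% v 90%, 80% and 70%. Over these:
- The protocol rule gives +2.0 to +22.4 points at q = 100%, and −2.8 to +8.4 at q = 50%.
- The SAP rule gives exactly 0 with depleted patients as denominator, and −1.0 to −16.8 with all patients. Neither SAP result depends on q.

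**Why the signs behave this way.** Write g for the depletion gap, MabThera minus SAIT101. The protocol-rule difference is g·(q − r), and the SAP all-patient difference is −g·r. The protocol rule therefore points toward the weaker-depleting arm only when q exceeds r. The proportion depleted shows g directly, whatever q and r are.

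**Scale.** At 67 per arm, 4.8 points is 67 × 0.048 ≈ 3 patients and 3.2 points is about 2. The 95% half-width for the first difference is 1.96 × √[(0.412 × 0.588 + 0.460 × 0.540)/67] ≈ 17 points.

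**The case against.** - **Recovery presupposes loss.** The SAP speaks of counts that have returned to a level. Scoring a never-depleted patient as recovered mixes fast recovery with failure to deplete. This stands as a reason to report recovery among depleted patients. It does not stand as a reason to replace the protocol's definition without declaring it or stating a denominator.
- **Weaker depletion would show elsewhere.** A reader might infer that a product depleting fewer patients could pass through the report looking equal or longer-acting. The documents do not support that. SAP 14.1 plans observed CD19+ counts and changes from baseline by treatment and time point, with 95% CIs and plots. SAP 14.2 plans AUECs over each dosing interval and to Weeks 12, 28 and 52, with mean differences and 90% CIs. SAP 17.6 itself adds counts by visit and listings. This objection stands and confines the point to the recovery output.
- **The reversal needs the less natural reading.** A precondition on assessment most naturally means that never-depleted patients are not assessed. That is so, but the text does not settle it. The table templates that SAP 7 mentions may settle it; they are not among the documents.
- **The illustration can flatter the protocol rule.** A patient who falls from 200 to 30 cells/µL is never depleted, yet is well below half of baseline. With q = 50% the protocol rule shows little and can change sign. This stands, and is why the depletion proportion is needed as well as the protocol-rule figure.
- **Nothing suggests a gap in depletion.** The one clinical B-cell comparison that the protocol cites, a 24-patient study in another lymphoma, reports changes of −7.7% and −8.0%. That is not a depletion rate, but it lends no support to a large gap.

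**Conclusion.** The point holds as a matter of definition and transparency. SAP 17.6 conditions a protocol endpoint on a drug effect after randomisation, SAP 2.6 does not declare it, and neither the proportion depleted nor the denominator is planned. The resulting figure departs from the protocol endpoint. It can mask a difference in depletion and, under one reading of the denominator, reverse its direction.

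The reach is small: one descriptive safety output, in about 67 patients per arm, with no comparison between arms attached. The CD19+ analyses in SAP 14 are unaffected. If depletion is near complete in both arms, the distortion is negligible. Every magnitude above rests on assumed rates, and the protocol-rule figures depend strongly on how many never-depleted patients meet the threshold. A reader might also infer that the protocol's definition is the dependable one and that recovery among depleted patients should be demoted. The arithmetic does not support that: each figure answers a different question, and neither replaces the depletion proportion. This is a change to consider.

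**What to change.** In SAP 17.6:
1. Report by arm the number and proportion of patients with CD19+ data who fall below 20 cells/µL after dosing. The present text does not require the low count to be post-dose, so a patient already below 20 at baseline could satisfy it with no drug effect.
2. Report recovery at Weeks 12, 20, 28, 36 and 52 twice: under the protocol definition in all patients with CD19+ data, and among depleted patients. State the denominator of each, making clear that it comes from the PK/PD sub-population.

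In SAP 2.6, list the added condition as a change from the protocol.

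The cost is a few table rows and some wording. It needs no new data and does not touch the primary analysis.

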## 17.7. OTHER SAFETY ASSESSMENTS

The following data will be listed only:

- Abnormal physical examination
- Pregnancy test
- TB test
- HBV testing
- New anti-lymphoma treatment

Document:

Author:

Version Number:

Version Date:

Final v1.0

10Sep2019

Template No: CS\_TP\_BS016 Revision 4

Effective Date: 01Apr2016

Reference: CS\_WI\_BS005

- ECOG Performance Score

## 18. Immunogenicity Outcomes

The immunogenicity analyses will be performed using the SAF.

### 18.1. ADA

The incidence of ADA and neutralizing antibody at Day 1 pre-dose and at Weeks 2 pre-dose, 3 pre-dose, 4 pre-dose, Week 5, 12, 20, 28, 36, and 52 (EOS) will be summarized by treatment group and visit.

- Incidence (%)= number of subjects with specific assessment result/ number of subject with available assessment results \* 100%

ADA and neutralizing antibody results by visit as well as the overall positive of ADA and neutralizing antibody from Day 1 will be summarized. Patients with at least one positive result up to Week 28 (or Week 52) from (and including) Day 1 will be considered as overall positive; Otherwise, patients without any positive result up to Week 24 (or Week 52) from (and including) Day 1 will be considered as overall negative.

For each treatment group, the proportion of response, 95% CI for the proportion, proportion difference between SAIT101 and MabThera®, standard deviation, and 95% CI for the proportion difference will be reported. The Wilson Score method will be used to calculate 95% CI.

- Response:
  - ADA positive
  - ADA negative
  - Neutralizing antibody positive
  - Neutralizing antibody negative

Listings for ADA assessments by patient will be provided.

---

Document:

Author:

Version Number:

Version Date:

Final v1.0

10Sep2019

Template No: CS\_TP\_BS016 Revision 4

Effective Date: 01Apr2016

Reference: CS\_WI\_BS005

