2.3.6 Immunogenicity Endpoints

- Incidence of human antichimeric antibody (HACA)
- Incidence of neutralizing antibody (if HACA is positive)

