- w To be performed by the central laboratory. On infusion visits, the sample should be collected pre-dose. Immunogenicity assessment is also planned when patients show signs or symptoms of immune-response-related adverse events including anaphylaxis (Section 6.4.3) and mucocutaneous reaction (Section 6.4.5)

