## 15. Exploratory Analysis of ADA on PK and PD

An exploratory statistical assessment of the impact of overall ADA status (positive or negative) on PK across treatments will be completed by adding this covariate to the model used in the primary statistical analysis.

Overall ADA status will be defined as ADA positive if a positive ADA result occurred at any timepoint up to Week 28 (for Week 28 analysis for PK and PD and for final analysis for PK only) or up to Week 52 (for PD, final analysis). Subjects without a positive ADA result at any timepoint are considered ADA negative.

The ratio of geometric means for ADA positive/ADA negative will be reported with the 90%

---

Document:

Author:

Version Number:

Version Date:

Final v1.0

10Sep2019

Template No: CS\_TP\_BS016 Revision 4

Effective Date: 01Apr2016

Reference: CS\_WI\_BS005

CI for this ratio. Descriptive statistics for rituximab concentrations and the primary PK parameters will also be presented by ADA status. Mean PK profiles will be plotted by treatment and ADA status on linear and semi-log concentration scales.

The impact of ADA on PD (observed CD19+ B cell counts) will be explored graphically. Mean PD profiles will be plotted by treatment and overall ADA status on a linear scale.

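### SAP 18.1 counts a Day 1 pre-dose positive as overall ADA positive, so the overall 'incidence' summary mixes pre-existing with drug-induced antibodies

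*SAP*

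**What the plan says.** The protocol lists immunogenicity among its secondary objectives (section 2.2). The endpoint in section 2.3.6 begins "Incidence of human antichimeric antibody (HACA", followed by the incidence of neutralising antibody in HACA-positive patients. Protocol 8.10 asks only for a summary by visit and treatment group in the safety set.

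SAP 18.1 adds an overall status. Overall positive means "Patients with at least one positive result up to Week 28 (or Week 52) from (and including) Day 1". The same section places the first sample before dosing: "The incidence of ADA and neutralizing antibody at Day 1 pre-dose and at Weeks 2 pre-dose". Protocol Table 1 (section 3.1, footnote w) agrees: "On infusion visits, the sample should be collected pre-dose". Incidence is "number of subjects with specific assessment result/ number of subject with available assessment results", so baseline positives stay in both numerator and denominator. For ADA and neutralising antibody, positive and negative, "95% CI for the proportion difference will be reported", using the Wilson score method.

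The complementary class in SAP 18.1 is worded as "patients without any positive result up to Week 24 (or Week 52"), although the positive class runs to Week 28.

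Baseline ADA status is tabulated as a baseline characteristic (SAP 9). ADA results are also summarised by visit, with Day 1 shown, and listed by patient (SAP 18.1).

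**The concern.** An incidence endpoint should count antibodies that appear after exposure. The overall status in SAP 18.1 counts antibodies present at any time, including before exposure. Pre-existing positives carry no information about the products' immunogenicity. They bring the two arms closer together and add variance to the comparison.

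In a biosimilar trial that error is not conservative, because a blurred difference reads as similarity. The SAP already applies the right principle to adverse events: section 17.1 does not count a pre-existing event as treatment-emergent unless it worsens. ADA has no equivalent rule.

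**Working it through.** **Inputs.** The documents give 154 patients per arm with 1:1 allocation (Protocol 8.4, SAP 2.3). They give no baseline ADA rate, no expected ADA rate, and no ADA power or margin. I therefore assume emergent rates of 10% v 3% among baseline-negative patients and an equal baseline prevalence b in both arms, varied from 0 to 10%. I also assume that all 154 per arm contribute a Day 1 and a post-dose result.

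**The plan's own figure.** The only stated figure behind n = 154 is 83% power for ORR equivalence at 77% in both arms, with a margin of ±16 points. SE = √(2 × 0.77 × 0.23 / 154) = 0.0480. Power = 2Φ(0.16/0.0480 − 1.96) − 1 = 83.1%. Full enumeration with the unstratified Newcombe-Wilson interval gives 84.0%. The figure reproduces, so I take 154 as given.

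**Formulae.** Under SAP 18.1 the overall rate in an arm with emergent rate p is b + (1−b)p. With equal b, the between-arm difference is (1−b)(p₁ − p₂). I compare this, with n = 154, against the treatment-emergent difference p₁ − p₂ among the 154(1−b) baseline-negative patients per arm. Both use the unpooled z and a normal 95% half-width.

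At b = 5% the rates under SAP 18.1 are 0.05 + 0.95 × 0.10 = 14.5% and 0.05 + 0.95 × 0.03 = 7.85%. The difference is 6.65 points, SE = √[(0.145 × 0.855 + 0.0785 × 0.9215)/154] = 0.0357, and z = 1.86. For the treatment-emergent definition, SE = √[(0.10 × 0.90 + 0.03 × 0.97)/(154 × 0.95)] = 0.0285 and z = 0.07/0.0285 = 2.45.

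| b (assumed) | SAP 18.1 rates | SAP 18.1 difference ± half-width (points) | z, SAP 18.1 | Emergent difference ± half-width (points) | z, emergent |
|---|---|---|---|---|---|
| 0 | 10.0% v 3.0% | 7.0 ± 5.5 | 2.52 | 7.0 ± 5.5 | 2.52 |
| 2% | 11.8% v 4.9% | 6.9 ± 6.1 | 2.19 | 7.0 ± 5.5 | 2.49 |
| 5% | 14.5% v 7.9% | 6.65 ± 7.0 | 1.86 | 7.0 ± 5.6 | 2.45 |
| 10% | 19.0% v 12.7% | 6.3 ± 8.1 | 1.52 | 7.0 ± 5.7 | 2.39 |

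Most of the loss is in precision. At b = 5% the difference falls by 5%, while the half-width rises by about a quarter (5.6 to 7.0 points).

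**Other assumed rates.** The chance that the unstratified Newcombe-Wilson 95% CI excludes zero, by full enumeration, is shown as SAP 18.1 v treatment-emergent:

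| Emergent rates | b = 2% | b = 5% | b = 10% |
|---|---|---|---|
| 10% v 2% | 73% v 86% | 57% v 85% | 41% v 83% |
| 15% v 5% | 76% v 84% | 66% v 83% | 52% v 81% |
| 20% v 10% | 64% v 68% | 56% v 67% | 46% v 66% |

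**Chance imbalance.** Even with the same true b, the observed baseline-positive proportions differ between arms with a 95% range of ±1.96√(2b(1−b)/154). That is ±3.1 points at b = 2%, ±4.9 at 5% and ±6.7 at 10%. The observed overall difference can therefore be pushed up or down, not only shrunk.

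**The case against.** **Size.** The loss depends entirely on a baseline rate that the documents do not give, and it is nil at b = 0. Protocol 3.2.2 excludes prior rituximab or other monoclonal antibodies (criterion 1) and hypersensitivity to murine products (criterion 14). Either may keep b low, although neither rules out positive assay results at baseline. With 10% v 3%, z stays above 1.96 until b is near 4%. This stands, and it is why the size is given only as a conditional range.

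**Visibility.** Baseline status, by-visit results and listings let a reader see how many patients were positive on Day 1. This softens the point but does not remove it. The overall figure stays mixed, and a baseline positive that persists also appears in the post-dose visit summaries.

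**Stronger readings that the documents do not support.**

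- *The CI is certainly built on the mixed status.* SAP 18.1 does not say whether the difference and CI apply to overall status, to each visit or to both.
- *The comparison collapses because the ratio of rates falls from 3.3 to 1.8 at b = 5%.* The arithmetic is right, but the planned statistic is a difference, which moves only from 7.0 to 6.65 points. No ADA hypothesis test is specified.
- *The negative class is really cut at Week 24.* The sentence makes negative the complement of positive, and a Week 28 positive is expressly positive. Week 24 is also not an ADA sampling visit. It reads as a slip.
- *The any-time status in SAP 15 and 16.3 is wrong for the same reason.* Section 15 says "Subjects without a positive ADA result at any timepoint are considered ADA negative", and section 16.3 likewise does not exclude Day 1. Those exploratory analyses ask whether antibody presence goes with exposure, B-cell counts or response, and pre-existing antibody can matter there. A treatment-emergent status would leave baseline-positive patients in neither class. Any-time status is a defensible choice in those sections.

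**Conclusion.** The point holds for SAP 18.1. Followed as written, the overall ADA and neutralising antibody summary is a prevalence that includes pre-dose positives, whereas the protocol's endpoint is incidence. Any between-arm difference and CI based on that status is diluted by (1−b), less precise, and exposed to chance baseline imbalance.

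The size is unknown. It runs from nothing at b = 0 to a drop in z from 2.39 to 1.52 at b = 10%, assuming 10% v 3% emergent rates, equal b in both arms and 154 evaluable patients per arm. The direction of the dilution follows from the definition alone; the numbers do not.

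A reader might infer that the efficacy conclusion is at risk. It is not: the primary ORR analysis, its margin and its sample size do not use ADA status, and the ADA subgroup analysis of ORR is exploratory.

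**What to change.** In SAP 18.1:

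1. Define overall ADA incidence as treatment-emergent: negative at Day 1 pre-dose and at least one post-dose positive up to Week 28 (or Week 52), among patients with at least one post-dose result. Define neutralising antibody incidence in the same way. Protocol 5.3 runs the neutralising assay only on samples in which HACA is detected, so say that an ADA-negative Day 1 sample counts as neutralising-antibody negative.
2. State that the between-arm difference and 95% CI use this status, and whether they are also given by visit.
3. Report baseline-positive patients separately by arm, with their post-dose results. Neither document mentions titres, so a boosted response cannot be assumed to be measurable.
4. State how patients with a missing Day 1 sample are handled.
5. Correct 'Week 24' to 'Week 28'.

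Keep the any-time status in SAP 15 and 16.3. Treatment-emergent status may be added there as a supplementary analysis.

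The cost is a few lines of SAP text and a derived flag for each antibody type. The Day 1 sample is already collected, so no new data are needed. The change should be fixed before treatment codes are known.
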